13.4.4 Guidelines for Reporting Pregnancies

All female subjects of childbearing potential must use an effective method of birth control during the study, to include 2 weeks after last visit, in a manner such that risk of contraceptive failure is minimized. Abstinence is allowed as a birth control method.

During the study, all female subjects of childbearing potential should be instructed to contact the Investigator immediately if they suspect they might be pregnant (eg, missed or late menstrual period). Female subjects who become pregnant during the study will be followed until completion of pregnancy. Every effort will be made to obtain the health status of the mother and infant or fetus (in cases of miscarriage or therapeutic abortion) at term. Pregnancy itself is not considered an AE.

All confirmed pregnancies must be reported to the medical monitor and CRO via confirmed facsimile or email transmission and must be submitted on a Pregnancy Report Form to the Sponsor or designee within 24 hours of the Investigator's awareness of the pregnancy.

Although pregnancy occurring in a clinical study is not considered to be an AE or SAE, any pregnancy complication, spontaneous abortion, or elective termination of a pregnancy, for medical reasons, will be recorded as an SAE. Any serious complication or event resulting from the pregnancy should be reported to the Sponsor within 24 hours on a SAE/UADE Report Form along with the Pregnancy Report Form.

The contacts for reporting pregnancies are:

14.0 STATISTICAL METHODS

14.1 Study Endpoints

14.1.1 Primary Effectiveness Endpoint

The primary effectiveness endpoint will be statistical non-inferiority with respect to mean distance high-contrast logMAR lens VA for each eye between the test and control lenses. For each eye, distance high-contrast logMAR lens VA will be averaged over all scheduled visits as the primary endpoint. A non-inferiority upper bound of 0.06 (3 letters) will be used to assess the difference (test – control) in mean logMAR lens VA.

14.1.2 Primary Safety Endpoint

The primary safety endpoint will be statistical non-inferiority with respect to the proportion of eyes with any slit lamp findings Grade >2 at any follow-up visit between the test and control lenses. A non-inferiority upper bound of 0.10 will be used to assess the difference (test – control) in proportions of slit lamp outcomes.

14.2 Hypotheses

14.2.1 Primary Effectiveness Endpoint

The null hypothesis (H_0) for the primary effectiveness endpoint is that the difference between the test mean (μ_T) and the control mean (μ_C) in distance high-contrast logMAR lens VA averaged over all scheduled visits is ≥ 0.06 . The alternative hypothesis (H_1) is that the difference is <0.06.

$$H_0: \mu_T - \mu_C \ge 0.06$$

$$H_1$$
: $\mu_T - \mu_C < 0.06$

14.3 Primary Safety Endpoint

The null hypothesis (H_0) for the primary effectiveness endpoint is that the difference between the test (π_T) and the control (π_C) in the proportion of eyes with any slit lamp findings Grade >2 at any follow-up visit is ≥ 0.10 . The alternative hypothesis (H_1) is that the difference is <0.10.

$$H_0: \pi_T - \pi_C \ge 0.10$$

$$H_1$$
: $\pi_T - \pi_C < 0.10$

14.4 Sample Size

Sample size calculation inputs (eg, standard deviations [SDs] and expected percentages) were estimated based on the results of a previous clinical trial evaluating the test lens.¹

14.4.1 Primary Effectiveness Endpoint

When the sample sizes in the groups are 100 eyes and 50 eyes, a 2-group 0.05 one-sided t-test will have 99% power to reject the null hypothesis that the test lens is inferior to the Clinical Study Protocol

control lens (the difference in means, μ_T - μ_C , is ≥ 0.060) in favor of the alternative hypothesis that the test lens is non-inferior to the control lens, assuming that the expected difference in means is 0.000 and the common SD is 0.076.

14.4.2 Primary Safety Endpoint

With 50 eyes in the control group and 100 eyes in the test group, the upper limit of the observed 1-sided 95% confidence interval will be expected to be <0.100 with 99% power when the control proportion, π_C , is 0.012 and the test expected proportion, π_T , is 0.012; results are based on 10000 simulations using the Newcombe-Wilson score method to construct the confidence interval.²

14.4.3 Overall Power and Sample Size

Assuming independence of the primary endpoints, the overall power of the study to show non-inferiority for both endpoints is 98%. Accounting for up to 10% losses, approximately 168 eyes (84 subjects) should be enrolled.

14.5 Randomization

Subjects will be randomized to 1 of 2 treatment arms in a 2:1 ratio (test:control), wearing either test or control lenses in both eyes for the duration of the study. Randomization will be stratified by investigational site.

Subjects will be randomized, after they are deemed eligible to participate, according to subject-specific randomization information provided by the randomization system.

14.6 Study Populations

14.6.1 Intent-to-Treat Population

The intent-to-treat (ITT) population will consist of all randomized eyes. Eyes will be included in treatment groups according to the treatments to which they were randomized for ITT population summaries.

14.6.2 Per-Protocol Population

The per-protocol (PP) population will consist of all randomized eyes without the following important protocol deviations:

- Ineligible when randomized
- Not dispensed study lenses
- Use of an incorrect lens type (eg, due to improper randomization, erroneous dispensing, return to habitual lens brand, etc.)
- Use of a lens care system other than the lens care system dispensed
- Failure to wear the assigned lenses at least 80% of the expected days
- Failure to provide non-missing distance high-contrast logMAR lens VA data at all of the scheduled visits (Dispensing Visit and 1-Week, 1-Month, 2-Month, and 3-Month Visits)

Additional important protocol deviations may be identified prior to unmasking of the treatment assignments

14.6.3 Safety Population

The safety population will consist of all dispensed eyes. Eyes will be included in treatment groups according to the treatments that were actually dispensed to them for safety population summaries. If an eye uses both lens types, then the eye will be included in the test lens group for safety population summaries.

14.7 Statistical Analysis

A full declaration of planned statistical analyses will be documented in a formal statistical analysis plan (SAP). Any deviations from the SAP will be documented in the final study report.

14.7.1 Methods of Analysis

14.7.1.1 General

In general, data will be summarized by treatment group and visit as appropriate.

Eyes will be treated as independent. In other words, the correlation between eyes within subjects will be ignored.

Summaries for continuous variables will include the sample size, mean, SD, median, minimum, and maximum. Means and medians will be presented with 1 more decimal place than the recorded raw data. Standard deviations will be presented with 2 more decimal places than the recorded raw data. Minima and maxima will be presented with the same number of decimal places as the recorded raw data. Values with magnitude <1 will be presented with a leading zero to the left of the decimal (eg, 0.123 or 0.123).

Categorical data will be summarized using frequencies and percentages. Percentages will be presented with 1 decimal place. Percentages may not be presented when the count is 0. Unless otherwise specified, the denominator for percentages will be the number of non-missing values within the group being presented.

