9.5 Treatments

Approximately 56 subjects (112 eyes) will be randomized to receive Bausch + Lomb investigational custom samfilcon B lenses and approximately 28 subjects (56 eyes) will be randomized to receive Alden Optical HP Sphere contact lenses. Subjects will be assigned randomization numbers, according to the randomization system.

Subjects will wear their lenses on a daily wear basis for 3 months.

NOTE: Use of other contact lenses is not allowed during the study.

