14.7.1.2 Primary Effectiveness Analysis

Monocular distance high-contrast logMAR lens VA will be assessed at each scheduled visit (Dispensing Visit and 1-Week, 1-Month, 2-Month, and 3-Month Visits). VA will be converted to logMAR units. For each eye, logMAR VA will be averaged over all scheduled visits resulting in 1 value of "All Study" logMAR lens VA per eye.

"All Study" logMAR lens VA will be presented using continuous summary statistics for the PP population by treatment group in a table at the eye level. A 2-sided 90% confidence interval for the difference (test – control) in "All Study" logMAR lens VA will be constructed using an analysis of variance (ANOVA) model with fixed factors of treatment and site. If the upper limit of the confidence interval is \leq 0.06 then the null hypothesis will be rejected and the test lens will be statistically successful in this outcome.

The previous analysis will also be completed using the ITT Population as a sensitivity analysis. For this sensitivity analysis, missing logMAR VA values will be imputed 25

times using the Markov chain Monte Carlo (MCMC) method. The seed used to generate the imputations will be 1187871241. The results of analyses (as described above for the PP population) by imputation will be combined to produce a 2-sided 90% confidence interval for the difference between treatments.

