14.7.1.3 Primary Safety Analysis

Graded slit lamp findings will be assessed at each scheduled follow-up visit (1-Week, 1-Month, 2-Month, and 3-Month Visits) and, optionally, at unscheduled visits. Each eye will be classified with respect to having 1 or more observations with Grade >2 (Yes, No) at any follow-up visit, including unscheduled visits.

The number and percentage of eyes with findings Grade >2 at any follow-up visit will be presented for the safety population by treatment group in a table. A 2-sided 90% confidence interval for the difference (test – control) between treatment groups will be constructed using the Newcombe-Wilson score method. If the upper confidence limit $\leq 10\%$ (0.10) then the null hypothesis will be rejected and the test lens will be statistically successful in this outcome. If both treatment groups have 0 eyes with a slit lamp finding Grade >2, then the confidence interval will not be calculable, the null hypothesis will be rejected, and the test lens will be statistically successful in this outcome.

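### Both primary analyses treat a subject's two eyes as independent although both wear the same randomised lens, so non-inferiority can be declared at more than the stated one-sided 5%

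*Combined protocol and SAP*

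**What the plan says.** Section 14.5 randomises subjects 2:1, each "wearing either test or control lenses in both eyes for the duration of the study". Treatment is therefore constant within a subject.

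Section 14.7.1.1 then sets the rule for all analyses: "Eyes will be treated as independent. In other words, the correlation between eyes within subjects will be ignored". The two primary analyses follow it:

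- **Effectiveness (14.7.1.2):** one averaged logMAR value per eye, analysed with an "analysis of variance (ANOVA) model with fixed factors of treatment and site". There is no subject term. Success means that the upper limit of the two-sided 90% interval is at most 0.06. The ITT sensitivity analysis repeats this model on imputed data.
- **Safety (14.7.1.3):** the proportion of eyes with a qualifying slit lamp finding. The interval for the difference "between treatment groups will be constructed using the Newcombe-Wilson score method", from eye counts, and is judged against 0.10.

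The analysis sets are also defined by eye: "The per-protocol (PP) population will consist of all randomized eyes without the following important protocol deviations" (14.6.2) and "The safety population will consist of all dispensed eyes" (14.6.3). Sections 14.4.1 to 14.4.3 count eyes as independent when they state powers of 99%, 99% and 98%. No ICC, design effect, subject effect or subject-level sensitivity analysis appears.

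**The concern.** When both eyes of a subject receive the same treatment, the second eye adds less information than a new subject would, unless the two eyes are uncorrelated. Counting every eye as a full observation understates the standard error. In a non-inferiority trial an interval that is too narrow favours the test lens. Site as a fixed factor cannot absorb correlation within a subject.

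Both primary success decisions are exposed. Section 14.7.2 dispenses with a multiplicity adjustment because both endpoints must succeed, but that argument needs each test to hold its own 5%.

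**Working it through.** **Inputs.** From 14.4.1: 100 and 50 eyes, one-sided 0.05, SD 0.076, true difference 0, margin 0.06. From 14.4.2: the same eye counts, rate 0.012 in both arms; the margin of 0.10 is in 14.1.2. From 9.5: 112 and 56 eyes (56 and 28 subjects) planned for randomisation. From 14.4.3: 10% losses. The ICC is not in the documents, so it is assumed at 0, 0.2, 0.5, 0.8 and 1.0.

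**1. The plan's own figures.** With independent eyes, effectiveness power by noncentral t is 99.8%. Safety power by exact enumeration is 99.9%. The overall figure is 0.99 × 0.99 = 98.0%, and 75 / 0.9 = 83.3, hence 84 subjects. The stated figures are consistent with independent eyes.

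**2. Effectiveness error.** With two eyes per subject,

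Var(difference) = SD² × (1 + ICC) × (1/100 + 1/50),

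while the ANOVA uses this without the factor (1 + ICC). At the margin, the chance of declaring success is 1 − Φ(1.645 / √(1 + ICC)). For ICC 0.8: 1.645 / √1.8 = 1.226, giving 11.0%. The planned treatment-plus-site ANOVA was also simulated (8 sites, 40,000 runs).

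| Assumed ICC | 0 | 0.2 | 0.5 | 0.8 | 1.0 |
|---|---|---|---|---|---|
| Formula | 5.0% | 6.7% | 9.0% | 11.0% | 12.2% |
| ANOVA, 100/50 eyes | 5.1% | 6.9% | 9.3% | 11.4% | 13.0% |
| ANOVA, 112/56 eyes | 4.9% | 6.7% | 9.3% | 11.5% | 13.0% |

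**3. Safety error.** Exact enumeration at a true difference of 0.10 (control 0.012, test 0.112), with P(both eyes affected) = p² + ICC × p(1 − p) and success when the upper limit is at most 0.10:

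| Assumed ICC | 0 | 0.2 | 0.5 | 0.8 | 1.0 |
|---|---|---|---|---|---|
| 100/50 eyes | 5.3% | 7.1% | 9.7% | 12.0% | 11.0% |
| 112/56 eyes | 4.7% | 6.2% | 8.2% | 10.0% | 10.6% |

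The test is discrete, so these values move with the eye counts. Over all subject counts from 50/25 to 56/28 the error is 5.8–7.3% at ICC 0.2 and 9.6–12.5% at 0.8. They also move with the control rate. With 112/56 eyes, the error passes 5% only above an ICC of about 0.04 at a 1.2% control rate, 0.18 at 0.5% and 0.32 at 0.1%. The excess already present at ICC 0 (5.3–5.7% with 100/50 eyes over control rates of 0.1–5%; 5.5–5.6% with 112/56 at 3–5%) comes from the interval method, not from correlation.

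**4. The both-endpoints rule.** Suppose effectiveness sits at its margin with ICC 0.8, and safety is truly non-inferior with about 99% power. The false-success rate is then about 0.99 × 11.0% = 10.9%.

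**5. Error of the corrected analyses.**

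- *Effectiveness, random subject effect* (REML, between-subject degrees of freedom, 50/25 subjects, 20,000 runs): 4.8 / 5.1 / 5.2 / 5.1% at ICC 0 / 0.2 / 0.5 / 0.8. With 8 of 75 subjects giving one eye: 4.6 / 4.8 / 5.1 / 5.0%.
- *Safety, Newcombe-Wilson with the eye-level proportion and n = subjects*, 1.2% control rate, ICC 0 / 0.2 / 0.5 / 0.8 / 1.0: 0.9 / 1.5 / 2.7 / 4.1 / 3.8% (50/25 subjects) and 0.9 / 1.5 / 2.5 / 3.6 / 4.6% (56/28). Over control rates of 0.05–5% the worst values are 5.1% and 5.7%, both at ICC 1.0 with control rates of 3–5%.

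**The case against.** The strongest reply has four parts.

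- **The ICC is unknown.** All inflation figures rest on assumed values, and the earlier study behind the sample-size inputs is not available here. This stands as a limit on the size. It does not rescue the plan: nothing in the documents supports an ICC of zero, and a subject effect estimates the correlation from the data.
- **The practical effect on effectiveness is small.** At SD 0.076 the 90% half-width is about 0.022 with independent eyes and 0.031 at ICC 1. The largest passing observed difference therefore moves from about 0.038 to 0.029 logMAR, less than half a letter on the plan's scale (0.06 = 3 letters), and the plan expects a difference of zero. This is fair. The inflation matters when the true difference is near the margin, but that is the case the 5% limit exists to control.
- **The safety excess is smaller than the 100/50 row suggests.** That row starts at 5.3%. Section 14.6.3 counts all dispensed eyes, so losses after dispensing do not shrink the set and 112/56 is the closer case. At a 0.1% control rate and ICC 0.2 its error is 4.2%. This stands, and the safety claim is limited accordingly.
- **Section 14.7 defers full detail to a formal SAP.** No text in the documents overrides the independence rule, which is explicit.

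**Conclusion.** The concern holds, and the plan should be changed before the analysis. For effectiveness, any positive between-eye correlation takes the one-sided error above 5%: 6.7% at ICC 0.2 and 11.0% at 0.8 by formula. For safety, at the planned 1.2% rate and the closer case of 112/56 eyes, the error rises from 4.7% at ICC 0 to 6.2% at 0.2 and 10.0% at 0.8. Whether it passes 5% depends on the ICC, the eye counts and the control rate. The direction follows from the design; the size rests on the assumed ICC and, for safety, on the paired-eye model used. The stated powers share the same unsupported assumption, but loss of power is the lesser problem.

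**What to change.** 1. **Section 14.7.1.1:** delete the independence rule.
2. **Effectiveness:** keep the eye-level values, treatment, site and the 0.06 margin. Add a random subject effect with between-subject degrees of freedom. This also handles subjects with only one per-protocol eye. Use the same model in the ITT sensitivity analysis, and state whether the imputation uses the fellow eye.
3. **Safety:** keep the eye-level proportion and the 0.10 margin, but compute the Newcombe-Wilson limits with the number of subjects per arm as the sample size (ICC set to 1). State how to count a subject with one dispensed eye, or with eyes in different groups. With no events the upper limit is 0.051 (50/25 subjects) or 0.046 (56/28), so the plan's zero-event outcome is unchanged.
4. **Sections 14.4.1 to 14.4.3:** restate in subjects, with an assumed ICC and its range.

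**Cost.** Wording and a few lines of code, wider intervals, and a conservative safety test when the true ICC is low. With no control events, at most 3 affected test eyes pass instead of 5. Power with 50/25 subjects is below. Effectiveness uses noncentral t with 73 degrees of freedom and SD 0.076 × √((1 + ICC)/2). Overall is the product, as the plan assumes.

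| Assumed ICC | 0 | 0.2 | 0.5 | 0.8 | 1.0 |
|---|---|---|---|---|---|
| Effectiveness | 99.8% | 99.3% | 97.9% | 95.7% | 93.9% |
| Safety, 1.2% in both arms | 97.9% | 96.8% | 95.3% | 93.2% | 90.5% |
| Overall | 97.7% | 96.2% | 93.3% | 89.2% | 85.0% |
| Safety, 3% in both arms | 83.7% | 81.8% | 79.5% | 76.9% | 71.5% |
| Planned interval, 3% in both arms | 96.9% | 95.6% | 93.8% | 91.9% | 88.9% |

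Enrolment can stay at 84 under the 1.2% rate if the sponsor accepts these values; a 3% rate would call for another look.

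The subject-count interval is one valid choice. Dividing the eye count by (1 + ICC) held 4.3–4.8% error at ICC 0.2 and 0.8 with 93.2–99.6% power, but only with the ICC taken as known. Fixing it at 0.5 gave 5.8% error at a true ICC of 0.8 and 6.6% at 1.0 (50/25 subjects). Any alternative should be prespecified and its error shown over a range of ICCs.

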14.7.1.2 Primary Effectiveness Analysis

Monocular distance high-contrast logMAR lens VA will be assessed at each scheduled visit (Dispensing Visit and 1-Week, 1-Month, 2-Month, and 3-Month Visits). VA will be converted to logMAR units. For each eye, logMAR VA will be averaged over all scheduled visits resulting in 1 value of "All Study" logMAR lens VA per eye.

"All Study" logMAR lens VA will be presented using continuous summary statistics for the PP population by treatment group in a table at the eye level. A 2-sided 90% confidence interval for the difference (test – control) in "All Study" logMAR lens VA will be constructed using an analysis of variance (ANOVA) model with fixed factors of treatment and site. If the upper limit of the confidence interval is \leq 0.06 then the null hypothesis will be rejected and the test lens will be statistically successful in this outcome.

The previous analysis will also be completed using the ITT Population as a sensitivity analysis. For this sensitivity analysis, missing logMAR VA values will be imputed 25

times using the Markov chain Monte Carlo (MCMC) method. The seed used to generate the imputations will be 1187871241. The results of analyses (as described above for the PP population) by imputation will be combined to produce a 2-sided 90% confidence interval for the difference between treatments.

